 - iv. Frequency of BFR Training: 6 days per week phase 1, 3 days per week phases 2 and 3
 - v. Frequency of clinic visits PT: 1 day per week for 12 weeks and then as needed
 - vi. Intervention Group: The following exercises outlined are the specific exercises that will be performed in addition to SOC. These exercises will be completed at home without professional supervision. The fitness app by SAGA is able to guide the user, and occlusion pressure is set manually by the PT at their first PT visit. Only these exercises will involve the use of the BFR cuff. Appropriate training on how to use the device will occur at the time of consent (approximately 20 minutes) and as requested by subject. The BFR cuff will be applied to the proximal thigh of the surgical leg beginning these specific exercises. 80% occlusion pressure will be determined by PT's in clinic through the use of a Delphi unit. Subjects will then be able to use the Saga Fitness app to adjust this pressure if it differs from the automatic calibrated pressure.
 1. Phase 1 (post operative weeks 0-2)
 - i. No BFR to be performed, subjects will follow standard protocol
 2. Phase 2 (weeks 3-6)
 - a. Dosage: 80% LOP. 30x15x15x15 repetitions with 30 sec rests between sets. At least 1 min rest between exercises with occlusion OFF
 - b. Frequency: All 3 resistive exercises performed at least 6 days per week. The first of these sessions will be performed in clinic supervised by PT to assess LOP and form prior to performance at home
 - c. Exercises:
 - i. Week 3: quadriceps set, gluteal set, hamstring set

- ii. Week 4: short arc quad, bridge, standing hamstring curl
 - iii. Week 5: straight leg raise, side-lying abduction, bridge on ball or chair
 - iv. Week 6: double leg squat, long arc quad, double leg RDL
3. Phase 3 (weeks 7-12)
- a. Dosage: 80% LOP . 30x15x15x15 repetitions with 30 sec rests between sets. At least 1 min rest between exercises with occlusion OFF
 - b. Frequency: All 3 resistive exercises performed at least 3 days per week. The first of these sessions will be performed in clinic supervised by PT to assess LOP and form prior to performance at home
 - c. Exercises:
 - i. Weeks 7-12: Single leg step up/squat progression (weigh progression as tolerated), single leg RDL (weight progression as tolerated), long arc quad (band progression as tolerated)
4. Phase 4 (12+ weeks)

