- a. Prescribed BFR intervention will be discontinued at 12 weeks and participants will progress per standard protocol for the remainder of their rehabilitation course. The subject will have the option to purchase a personally BFR cuff after the conclusion of the 12-week intervention. Usage post intervention time will be tracked and recorded via a PatientIQ survey at all follow-up time points.
- vii. Control Group
- 1. Control group will follow the standard of care outlined in Appendix A for both in clinic and at home exercises.
- viii. Criteria for progression within the BFR specific exercise protocol
- 1. Regardless of functional performance, patients will not be allowed to progress ahead of the time-based exercise prescription in the BFR protocol. However, if the treating therapist determines that the current week's exercise prescription is too difficult for the patient, they may return to the prior week's exercise set until able to advance.

Phase	Timepoint	Exercises	Measurements	PROs
0	Pre-op/ Surgery Day 0	None	None	*Consent All PROs
I	Week 1 Day 1-7	None	Knee Extension °; Knee Flexion °; Swelling; Gait; ROM Knee; Flexibility; Functional Testing	
	Week 2 Day 8-14	None	Knee Extension °; Knee Flexion °; Swelling; Gait; ROM Knee; Flexibility; Functional Testing	
II	Week 3 Day 15-21	[80% LOP] quadriceps set, gluteal set, hamstring set {30x15x15x15x15}	Knee Extension °; Knee Flexion °; Swelling; Gait; ROM Knee; Flexibility; Functional Testing	All PROs

	Week 4 Day 22-28	[80% LOP] short arc quad, bridge, standing hamstring curl {30x15x15x15x15}	Knee Extension °; Knee Flexion °; Swelling; Gait; ROM Knee; Flexibility; Functional Testing	
	Week 5 Day 29-35	[80% LOP] straight leg raise, side-lying abduction, bridge on ball or chair {30x15x15x15x15}	Knee Extension °; Knee Flexion °; Swelling; Gait; ROM Knee; Flexibility; Functional Testing	
	Week 6 Day 36-42	[80% LOP] double leg squat, long arc quad, double leg RDL {30x15x15x15x15}	Knee Extension °; Knee Flexion °; Swelling; Gait; ROM Knee; Flexibility; Functional Testing	All PROs
III	Week 7 Day 43-49	[80% LOP] (holding weight/or band as tolerated) single leg step up/squat progression, single leg RDL, long arc quad {30x15x15x15x15}	Knee Extension °; Knee Flexion °; Swelling; Gait; ROM Knee; Flexibility; Functional Testing (@ 12 weeks will include strength)	
	Week 8 Day 50-56			
	Week 9 Day 57-63			
	Week 10 Day 64-70			
	Week 11 Day 71-77			
	Week 12 Day 78-84			All PROs E-Stim Use

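### The protocol contradicts itself on the experimental-arm BFR dose: training days per week in phases 1 and 2, and four versus five sets throughout

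*Protocol*

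**What the plan says.** **Frequency.** Section 4.c.iv reads "Frequency of BFR Training: 6 days per week phase 1, 3 days per week phases 2 and 3". Section 4.c.vi then goes phase by phase:

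- Phase 1, weeks 0-2: "No BFR to be performed, subjects will follow standard protocol".
- Phase 2, weeks 3-6: "All 3 resistive exercises performed at least 6 days per week".
- Phase 3, weeks 7-12: "All 3 resistive exercises performed at least 3 days per week".

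Section 4.c.vi also restricts the cuff to the exercises it lists ("Only these exercises will involve the use of the BFR cuff"), and it lists none for phase 1. The schedule table at the end of Section 4.c shows no exercises in weeks 1 and 2. It gives no days per week for any phase.

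**Sets.** For phase 2, Section 4.c.vi gives "Dosage: 80% LOP. 30x15x15x15 repetitions with 30 sec rests between sets", and it repeats the four-set scheme for phase 3. The schedule table adds a fifth set. Its week 3 entry is "quadriceps set, gluteal set, hamstring set {30x15x15x15x15", and the entries for weeks 4, 5 and 6 and for phase III carry the same five numbers. The table legend defines the braces as the repetitions in each set.

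**The concern.** These lines define the experimental treatment, so a therapist needs them to agree. In phase 1, Section 4.c.iv collides with an outright bar and is unlikely to be followed. Phase 2 is the realistic frequency risk: following 4.c.iv there would halve the minimum training frequency. The set conflict runs through both BFR phases, and the protocol has no rule for which version governs.

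The training is mostly unobserved: "These exercises will be completed at home without professional supervision". Patients will do what they are taught, and what they are taught starts from this document. If therapists read it differently, the arm receives a mixture of doses and the result cannot be tied to one regimen.

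A planned analysis is also touched. Under Secondary Analyses in the Data Analysis Plan (Section 5.e.ii), non-compliance with BFR means completing fewer than 80% of prescribed sessions. That rule needs one agreed count of prescribed sessions.

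**Working it through.** **Inputs, all from the protocol.** Phase lengths: phase 1 is 2 weeks (days 1-14 in the schedule table), phase 2 is 4 weeks (weeks 3-6) and phase 3 is 6 weeks (weeks 7-12). Days per week come from Sections 4.c.iv and 4.c.vi, sets from Section 4.c.vi and the table. The protocol states no total dose, so there is no stated figure to reproduce.

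**Sessions = days per week × weeks.**

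| Phase | Section 4.c.iv | Section 4.c.vi (minimum) |
|---|---|---|
| 1 | 6 × 2 = 12 | 0 |
| 2 | 3 × 4 = 12 | 6 × 4 = 24 |
| 3 | 3 × 6 = 18 | 3 × 6 = 18 |
| Total | 42 | 42 |

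The totals match only because 4.c.iv places 12 sessions in weeks when BFR is barred. Respecting the bar and keeping 4.c.iv for the later phases gives 12 + 18 = 30 sessions, and 30/42 = 71%.

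**Repetitions.**

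- Four sets: 30 + 3 × 15 = 75 per exercise; 3 × 75 = 225 per three-exercise session.
- Five sets: 30 + 4 × 15 = 90 per exercise; 3 × 90 = 270 per session.
- Ratio: 90/75 = 1.20.

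**Repetitions per week**, assuming a session under 4.c.iv contains the three exercises of 4.c.vi:

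| | Four sets | Five sets |
|---|---|---|
| Phase 2, 3 days (4.c.iv) | 3 × 225 = 675 | 3 × 270 = 810 |
| Phase 2, at least 6 days (4.c.vi) | 6 × 225 = 1,350 | 6 × 270 = 1,620 |
| Phase 3, at least 3 days | 3 × 225 = 675 | 3 × 270 = 810 |

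The extreme readings of phase 2 differ by 1,620/675 = 2.4. If 4.c.vi governs frequency, the remaining uncertainty is 1,350 against 1,620, or 20%.

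**Compliance cut.** Under 4.c.vi, 80% of 42 is 33.6, so 34 sessions are needed. A participant who trains 3 days per week through weeks 3-12 completes 30. That meets 4.c.iv in full for those weeks but is 71% of the 4.c.vi minimum, hence non-compliant. With 30 as the prescribed number, the cut would be 0.8 × 30 = 24.

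**The case against.** The strongest reply is that this is a drafting slip with an evident answer. Section 4.c.iv is a one-line summary. Section 4.c.vi is the detailed prescription, and a therapist must consult it to know which exercises to give. Its phase 1 bar is explicit and the table agrees. For the frequency conflict most of this stands, and it is why 4.c.iv is probably the wrong line. It does not make the contradiction harmless: 4.c.iv is the only item headed as the BFR frequency, and the table offers no help on phase 2. Section 4.b.ii, which describes BFR as given from week 0, adds to the confusion.

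The factor of 2.4 combines two separate discrepancies at their extremes. That is fair: it bounds the literal readings and is not the likely spread. It is also true that the literal session totals are equal, and that the compliance cut changes only on the mixed reading (phase 1 barred, 4.c.iv kept for phase 2). The set conflict does not enter that cut, because compliance counts sessions.

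On sets, one could argue that 4.c.vi should prevail, since it states the four-set scheme twice with rest intervals. But the table states five sets in all five of its BFR entries, so neither version looks like a stray error.

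Finally, training at consent, app guidance, a supervised first session in each BFR phase and weekly physiotherapy visits all limit the risk. None of them tells the therapist which figure to teach. The app settings and any patient handouts are not in the document, so whether patients would actually receive differing doses is unknown.

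**Conclusion.** The inconsistency is real and should be fixed. On frequency, Sections 4.c.iv and 4.c.vi conflict in phase 1 (12 sessions against none) and phase 2 (12 against at least 24) and agree in phase 3, apart from the words making it a minimum. On sets, Section 4.c.vi and the schedule table differ by 20% per exercise in both BFR phases, with no rule to choose between them.

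That 4.c.iv is the faulty line is an inference from the phase 1 bar, the cuff restriction and the table. The weekly repetition figures rest on the assumption that every session contains all three listed exercises. The primary intent-to-treat comparison at 3 months and the sample size do not depend on this point. The delivered dose and the reproducibility of the regimen do; per-protocol classification does if 4.c.iv is followed in phase 2.

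**What to change.** 1. Rewrite Section 4.c.iv to say: no BFR in phase 1; at least 6 days per week in phase 2 (weeks 3-6); at least 3 days per week in phase 3 (weeks 7-12). The prescribed minimum is then 0 + 24 + 18 = 42 sessions, and the 80% rule has one denominator.
2. Have the investigators choose four or five sets. State that scheme identically in Section 4.c.vi (both phases), in every BFR entry of the schedule table, and in the patient and therapist instructions.

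The cost is one corrected line and one clinical decision copied into the matching places. No additional data, visits or participants are needed.

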 8. Brief Resiliency Score (BRS): Range 1 (low resilience) – 5 (high resilience); MDC = Δ low (1-2.99) to normal (3-4.3) to high (4.31-5)
 9. ACL-RSI: Range 1 (low function) – 100 (high function); MDC = Δ 15.1 for short form version
 10. IKDC : Range 1 (low function) – 100 (high function); MDC = Δ 8.8 low to Δ 15.6 high
 11. All PROs are nationally validated measures.
- b. Description of Population to be Studied:
 - i. General: patients aged 16-60 years old with knee joint pain to be treated operatively with knee arthroscopy. Based off the power analysis for both knee extensor strength and Tegner, we will recruit at least 78 participants (39 per group).
 - ii. Timeframe: BFR protocol administered 0-12 weeks post operatively, but data will be collected up until 2 years post operatively. Patients may be consented at pre-op or will be consented in person before or during their first post-operative physical therapy appointment. After being consented, subjects will be contacted via email and/or text message to prompt survey completion.
 1. PRO's will be collected at:
 - a. Initial evaluation

- i. Form is sent 7 days before surgery with an 8-day window for completion
- b. 3 weeks
 - i. Form is sent 3 weeks after surgery with a 7-day window for completion
- c. 6 weeks
 - i. Form is sent 6 weeks after surgery with a 7-day window for completion
- d. 12 weeks
 - i. Form is sent 10 weeks after surgery with a 30-day window for completion
- e. 6 months
 - i. Form is sent 24 weeks after surgery with a 30-day window for completion
- f. 9 months
 - i. Form is sent 36 weeks after surgery with a 30-day window for completion
- g. 1 year
 - i. Form sent 365 days after surgery with a 30-day window for completion
- h. 2 years
 - i. Form sent 730 days after surgery with a 30-day window for completion

2. Strength, ROM and functional performance measurements will be collected at 6 weeks, 12 weeks, 6 months and at discharge.

- iii. Inclusion criteria: Patients with ACL reconstruction with quadriceps, hamstring, bone-patellar-bone or allograft graft, with/without meniscectomies. Patients must also have access to a smartphone device in order to utilize the SAGA BFR application for use. The application is free to use.

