- iv. Exclusion criteria: Bilateral knee surgeries to be performed within 12 weeks of each other, meniscus repairs, chondral lesion repair/transplants, ACL revisions that utilize contralateral autografts, MCL repairs, and the following BFR contraindications: deep vein thrombosis (DVT), pulmonary embolism, hemorrhagic/thrombolytic stroke, clotting disorders, hemophilia or taking blood thinners, pregnant or up to 6 months postpartum, untreated hypertension, untreated hypotension, rhabdomyolysis or recent traumatic injury, does not understand English, and the following BFR contraindications:
 - 1. Contraindications for BFR
 - Deep Vein Thrombosis (DVT)
 - Pulmonary Embolism
 - Hemorrhagic/Thrombolytic Stroke
 - Clotting Disorders
 - Hemophilia or taking blood thinners
 - Pregnant or up to 6 months post-partum
 - Untreated Hypertension
 - Untreated Hypotension
 - Rhabdomyolysis or recent traumatic injury

2. Exclusion criteria will be evaluated via the medical record as well as by the expert opinion of the physician.
 3. If at any point in the study a subject develops one of the above contraindications, they will be removed from the study.
 4. If a subject becomes pregnant while participating in the intervention portion of the study, they will be removed.
- c. Study Design and Research Methods
- i. Timeline: Treatment Protocol duration 12 weeks per participant beginning at first post operative physical therapy appointment in week 1 following knee arthroscopy. PRO's will be collected out to 2 years post-surgery and standard rehabilitation will follow the 12-week intervention period for both the control and experimental group. Study will be a 2-year timeline in total.
 - ii. Procedures: Patients will be randomized to control group, who will undergo Steadman Hawkins Clinic Denver's standard knee arthroscopy rehab protocol (see appendix) or to the intervention group, who will undergo standard rehab protocol with addition of BFR. Subjects will be randomized 1:1 for intervention vs. control and controlled for sex assigned at birth. SOC for surgeons will be standardized to prevent the need for randomization.
 - iii. Materials: Saga Fitness BFR cuffs will be utilized for this study. These are products that are designed for at home use and are directly available to the consumer. They are wireless, automated training cuffs that connect to the Saga Fitness app via Bluetooth where they are then controlled.

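### For patients consented before surgery, device training at consent implies that the arm is known before procedure-based eligibility is settled, and no randomisation time is stated

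*Protocol*

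**What the plan says.** - **Training.** Section 4.c.vi, which describes the intervention arm only, states: "Appropriate training on how to use the device will occur at the time of consent (approximately 20 minutes", with more on request. It also has the physical therapist set the occlusion pressure at the first PT visit.
- **Consent.** Section 4.b.ii gives two routes: "Patients may be consented at pre-op or will be consented in person before or during their first post-operative physical therapy appointment". The schedule table has one consent entry, in the row "Pre-op/ Surgery Day 0".
- **Randomisation.** Section 4.c.ii states: "Subjects will be randomized 1:1 for intervention vs. control and controlled for sex assigned at birth". It gives no time point, and neither does any other section.
- **Eligibility.** Inclusion (4.b.iii) accepts ACL reconstruction with or without meniscectomy. Exclusion (4.b.iv) lists "meniscus repairs, chondral lesion repair/transplants, ACL revisions that utilize contralateral autografts, MCL repairs". Exclusions are judged from the medical record and by the physician, at no stated time. The removal rules there cover contraindications that develop later and pregnancy. They do not cover an excluded procedure carried out at surgery.
- **Analysis.** Section 5.e.i makes the primary comparison intent-to-treat at 3 months.
- **Start of BFR.** The phase 1 text (weeks 0-2) says "No BFR to be performed, subjects will follow standard protocol", and the schedule table shows the first BFR exercises in week 3. But 4.c.iv assigns BFR on six days a week to phase 1, and 4.b.ii has BFR running from week 0.

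**The concern.** Training given only to the intervention arm cannot take place until the arm is known. If it is given at a pre-operative consent, allocation comes before surgery. Part of eligibility depends on what is done at surgery: a meniscectomy keeps the patient in and a meniscus repair takes the patient out.

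Two things are at stake. First, patients may be found ineligible after randomisation. Removing them departs from intent-to-treat, and keeping them puts patients outside the target population into the primary analysis. Second, the physician judges the exclusions, and nothing says that the physician is unaware of the arm; only the person measuring strength and function is described as blinded (5.c.i). If the arm is known when an operative finding is classified, removals need not be balanced between arms. Randomising after surgery avoids both problems.

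**Working it through.** **1. What the consent route implies.**

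| Consent route | Surgery done at consent? | If only the intervention arm is trained at consent | If everyone is trained at consent |
|---|---|---|---|
| Pre-op | No | Arm known before surgery | Future controls taught to use the device |
| At first post-operative PT visit | Yes | Arm known after surgery; eligibility can be checked first | Future controls taught to use the device |

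On the pre-op route each reading has a defect. Training everyone matters because 4.c.iii describes the cuffs as a home product sold directly to consumers, so controls could obtain and use them.

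**2. Is the pre-op route likely to be common?** Under 4.b.ii survey prompts follow consent, and the baseline form goes out 7 days before surgery with an 8-day window (day −7 to about day +1). A patient consented at the first PT visit in week 1 would largely miss it. This suggests that pre-op consent is the route the schedule assumes. It is an inference, and the documents give no split between the routes.

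**3. The plan's sample size (5.e.iii).** Inputs: mean changes 11 and 3 Nm, SDs 13 and 9, two-sided alpha 0.05, power 80%.
- Pooled SD = √((13² + 9²)/2) = √125 = 11.18.
- d = (11 − 3)/11.18 = 0.716, stated as 0.72.
- Two-sample t-test: 31.6, rounded up to 32 per group, 64 in total. This reproduces the plan.
- Inflation: 32 × 1.2 = 38.4, rounded up to 39 per group, 78 in total. This reproduces the plan. (Dividing by 0.8 gives 40 per group, 80 in total; the difference is small and not the issue here.)

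**4. The allowance.** 78 − 64 = 14 patients, and 14/78 = 17.9%. Post-randomisation removals would draw on the same 14 as ordinary dropout, unless further patients are recruited. Section 4.b.i sets 78 as a minimum, so that is open.

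**5. Illustration of scale only.** Assume that a share x of all randomised patients is removed for an excluded procedure, that 20% of the rest drop out, and that no one is replaced. The documents give no value for x. Evaluable number = 78 × (1 − x) × 0.8.

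| x (assumed) | Evaluable | t-test power |
|---|---|---|
| 0% | 62.4 | 79.4% |
| 5% | 59.3 | 77.3% |
| 10% | 56.2 | 75.0% |
| 20% | 49.9 | 69.7% |

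If allocation follows confirmation of eligibility, x is 0 by design.

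**6. Interval from allocation to divergence.** On the phase text and schedule table, BFR starts on day 15. From consent on the day of surgery that is 15 days. From day −7 (an assumed consent date, taken from the survey timing) it is 15 + 7 = 22 days. From a first PT visit on days 1-7 it is 8 to 14 days. These figures hold only if the phase text and table are the governing statements, which the protocol leaves in conflict.

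**The case against.** The strongest reply is that the protocol states no randomisation time, so nothing in it orders allocation before surgery. The post-operative consent route makes training at consent workable, and the training sentence could cover everyone. This stands against the stronger claim a reader might infer, that the text forces pre-surgical allocation. The text implies it for patients consented pre-op, if training is for the intervention arm as its heading indicates.

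A reader might also infer that excluded procedures are always unknown before surgery. The documents do not say so. Bilateral surgery and a contralateral-autograft revision are planned features, and an MCL repair may be. That meniscus or chondral repair is decided at operation is plausible but not stated.

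It can further be said that removal on an operative fact recorded before any BFR biases the comparison only if the arm influenced the surgical decision or its classification, and that the analysis set may be defined in a statistical analysis plan not shown. Both are fair, so it would be too strong to say that the intent-to-treat comparison is broken. But a rule for the analysis set written elsewhere would not change the order of consent, training and surgery that the protocol itself sets out. That order creates the problem.

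**Conclusion.** The point holds in limited form. For patients consented before surgery, the training and consent wording either places allocation ahead of confirmed eligibility or trains future controls on the device, and the protocol has no rule for an allocated patient who then has an excluded procedure. Patients consented at the first post-operative PT visit are not affected.

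The conclusion rests on two assumptions: that training is for the intervention arm, and that some excluded procedures are settled only at surgery.

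The number of patients at risk cannot be derived. The documents give neither a rate of excluded procedures nor the share consented pre-op, so the power figures above show scale and are not a forecast. Someone might infer that the whole allowance of 14 would be used up. That would need an assumed rate and no replacement, and 78 is only a floor.

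Nor can it be said that allocation precedes divergence by two to three weeks. That interval applies to the pre-op route alone and takes one side of the unreconciled statements on BFR in phase 1. The eligibility argument does not depend on how that conflict is settled.

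The change is worth making because it is specific, nearly free and removes the problem by design.

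**What to change.** 1. Keep both consent routes. State in 4.c.ii that randomisation takes place only after surgery, once eligibility is confirmed from the operative record, and no later than the first PT visit, where 4.c.vi has occlusion pressure set.
2. In 4.c.vi, place device training after allocation, for the intervention arm only, at an existing PT visit.
3. State in 5.e.i that every patient randomised after that check stays in the intent-to-treat set.
4. Separately, reconcile 4.b.ii, 4.c.iv, the phase 1 text and the schedule table on BFR in phase 1 before stating when the arms diverge.

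The cost is moving a 20-minute training to a PT visit and having the operative record to hand by then. No visit is added. Patients found ineligible at surgery are simply not randomised, so they do not count towards the 78.
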